5.7 Other Restrictions and Precautions (if applicable)

Not Applicable.

5.8 Deviation from Inclusion/Exclusion Criteria

Any significant event that does not comply with the inclusion criteria, exclusion criteria, study conduct, or study procedures will be documented as a deviation. Deviations will be documented and reported through the clinical monitoring of the trial. Deviations will be reported to the IRB/EC at the frequency required by your IRB/EC. Prospective approval of protocol deviations to recruitment and enrollment criteria, also known as protocol waivers or exemptions, is not permitted.

6 STUDY CONDUCT AND DESCRIPTION OF STUDY PROCEDURES

6.1 Study Materials

The following study materials will be provided to the site:

- Investigator File/Study Binder
- Drug Accountability Logs
- Sample source documents
- Subject Concomitant Medication Log
- Investigator Brochure
- Interactive Web-based Response System (IWRS) manual
- Electronic Case Report Forms (eCRF)
 - o Electronic Case Report Forms (eCRFs) will be prepared for all data collection fields
- Provisioned electronic devices (subjects have the option to use their own smartphone and download an application to report the daily evening reports)
- Drug administration instructions
- Laboratory kits and laboratory manual
- ECG machine and instructions
- Serious Adverse Event (SAE) forms and Serious Adverse Events (SAE) Reporting instructions
- Pregnancy surveillance forms and reporting instructions
- S-STS source document
- MIDAS source document
- MSQ source document
- CGI-c source document

- Single use, disposable nasal speculums provided upon request
- Study system access:
 - o Electronic Data Capture (EDC) tool to submit study data to Sponsor/ CRO
 - o IWRS
 - Central Laboratory
 - o eCOA
- Handheld devices

The subject will report daily evening migraine reports electronically. The primary reporting method will be either through a provisioned device supplied by the eCOA vendor or the subject's personal device. If the subject is unable to report in the provisioned device or personal device, the subject will also have the option to complete the daily evening migraine reports in a password protected web portal. The web portal should be used as the secondary or back-up reporting method. If subject compliance with the daily evening migraine reports is low, the subject may be offered a provisioned device to assist with increased compliance.

6.2 Eligibility Assessments

Informed consent, inclusion/ exclusion criteria including medical history, migraine history assessment, concomitant medications, laboratory assessments, ECG, daily electronic evening reports as outlined in Table 1.

6.3 Safety Assessments

6.3.1 Vital Signs and Physical Measurements (Height and Weight)

Body weight and height will be recorded at the scheduled visits as outlined in Table 1.

6.3.2 Electrocardiogram (ECG)

A standard 12-lead ECG will be recorded at the screening visit and at the scheduled visits as outlined in Table 1. A central ECG service will be utilized for all ECGs. The over read from the central ECG vendor should be used to determine eligibility for the study. The Investigator will determine if any abnormalities are of clinical significance.

6.3.3 Physical Exam

Subjects will undergo a physical examination at screening at ET (Table 1). The directed physical exam should be guided by the subject's signs and symptoms.

6.3.3.1 Nasal Inspection

The nasal passages and turbinates will be visually inspected by the Investigator or medically qualified delegate with a nasal speculum or otoscope at visits specified in Table 1 to detect evidence of significant nasal conditions that may affect the administration or absorption of the nasal product (e.g. severe septum deviation, nasal deformity or blockage, inflammation, perforation, mucosal erosion or ulceration, polyposis, nasal trauma). Nasal findings will be recorded as appropriate and followed until resolution.

6.3.4 Laboratory Assessments

The investigator must review all laboratory reports, document this review, and record any clinically relevant changes occurring during the study in the AE section of the CRF (see guidance in Section 8.3.2). The laboratory reports must be filed with the source documents. Clinically significant abnormal laboratory test findings are those which are not associated with the underlying disease, unless judged by the investigator to be more severe than expected for the subject's condition.

All laboratory tests with abnormal values considered to be clinically significant during participation in the study should be repeated until the values return to normal or baseline or are no longer considered clinically significant by the investigator or medical monitor.

If such values do not return to normal/baseline within a reasonable period of time judged by the investigator, the etiology should be identified, and the sponsor notified.

All protocol-required laboratory assessments must be conducted in accordance with the laboratory manual and Table 1.

If laboratory values from non-protocol specified laboratory assessments performed at the institution's local laboratory require a change in subject management or are considered clinically significant by the investigator (e.g., SAE or AE or dose modification), then the results must be recorded in the CRF.

6.3.4.1 Safety Laboratory Testing

Blood and urine samples will be obtained as outlined in Table 1 for clinical laboratory evaluations. A central laboratory vendor will be utilized for this study and a laboratory manual will be provided to each site. If possible, subjects should be fasting for a minimum of 8 hours

prior to all blood draws. However, if a subject is not fasting at a given visit, the blood draw should still be performed, and the non-fasting status should be documented.

Clinical Safety Labs:

- **Hematology**: Hemoglobin, hematocrit, red blood cell count, white blood cell count with differential, and platelets.
- Chemistry: Sodium, potassium, chloride, bicarbonate, calcium; glucose, HbA1c, BUN (urea), serum creatinine, uric acid, LDH, total protein, albumin, CK (elevations in CK >5x ULN may have further CK fractionation tests performed).
- eGFR using the estimated MDRD formula (calculated at central lab)

LFTs: AST, ALT, alkaline phosphatase, and bilirubin (Total, Direct, Indirect)

Lipid panel: total cholesterol, LDL cholesterol, HDL cholesterol, triglycerides

Urinalysis: pH, specific gravity, ketones, nitrites, urobilinogen, leukocyte esterase, protein, glucose and blood. If blood, protein or leukocytes are positive, reflex to microscopic examination.

Urine Drug Screen: For drugs of abuse including but not limited to cocaine, amphetamines, barbiturates, opioids, PCP, and THC.

FSH: For WOCBP at screening, to determine WOCBP status

Reflex tests:

• If ALT or AST ≥ 3x ULN OR total bilirubin ≥ 2x ULN at any visit after the baseline visit, the central laboratory will perform reflex tests that may include: CK, GGT, and anti-viral serologies. Subjects may have to return to the study site to provide additional blood samples for these laboratory tests.

Additional laboratory tests may be required.

6.3.4.2 Pregnancy Testing

Pregnancy tests will be conducted (serum or urine), when appropriate and as outlined in Table 1.

6.3.5 Sheehan Suicidality Tracking Scale (S-STS) (if applicable)

The Sheehan STS (S-STS) is a prospective, subject self-reported or clinician administered rating scale that contains 16 questions to track both treatment-emergent suicidal ideation and behaviors 14,15 The S-STS will be completed on a paper form at the site. At the screening visit, the recall period for completing the S-STS is 30 days prior; at all other visits, the recall period for completing the S-STS is since the last visit. Any responses other than 0 must be immediately evaluated by the investigator. If the investigator determines that a subject is at risk of suicide or self-harm, appropriate measures to ensure the subject's safety and obtain mental health evaluation must be implemented. For discussion on a study specific basis: In such circumstances, the subject must immediately be discontinued from the study. The event should be recorded as either an AE or SAE as determined by the investigator and reported within 24 hours to the Sponsor.

Any subject with a response greater than 0 to any question, excluding Question 2, must be immediately discontinued from the study. Subjects with a response of 1 ("a little") to Question 2 will be discontinued per the investigator's assessment or if the response persists. Subjects with a response greater than 1 on Question 2 will be discontinued from the study immediately.

S-STS may be completed over the phone with the exception of the following visits: Screening, Pre-Baseline, Week 4, Week 24, EOT, and Follow-up Safety.

6.4 Efficacy Assessments

Not applicable.

6.5 Other Assessments

6.5.1 Daily Migraine Assessment of Intensity and Frequency

The number of migraine days and intensity of migraine attacks during the period that subjects are treated with zavegepant relative to the observation phase will be analyzed.

6.5.2 Migraine-Specific Quality of Life Questionnaire v 2.1

Impact of treatment on subject-reported quality of life will be assessed using the Migraine-Specific Quality of Life Questionnaire v 2.1 (MSQ v 2.1). The MSQ is a 14 item instrument that has been validated in 3 domains: role function – restrictive, role function – preventive, and emotional function. ¹⁶

6.5.3 Preference of Medication

The Preference of Medication (PoM) is a subject-rated, 5-point scale that measures the preference of the study drug compared to the previous medications to treat migraine pain. The PoM will be completed electronically.

6.5.4 Satisfaction with Medication

The Satisfaction with Medication (SM) is a subject-rated 7-point scale that measures satisfaction with the study drug to treat migraine headaches. The SM will be completed electronically.

6.5.5 Migraine Disability Assessment (MIDAS) Questionnaire

The Migraine Disability Assessment (MIDAS) is a retrospective, subject-reported, 5 item questionnaire that measures headache-related disability as lost days due to headache from paid work or school, household work, and non-work activities over a 3-month period. The MIDAS will be completed on paper.¹⁷

6.5.6 Clinical Global Impression – Change (CGI-c) Scale

The Clinical Global Impression-change (CGI-c) scale is an observer-rated, 7-point scale that measures subject total improvement relative to the investigator's past experience with other subjects with the same diagnosis, with or without collateral information. The CGI-c will be administered by the investigator, or designee who has been trained on administration, and will be completed on a paper form.¹⁸

6.6 Early Discontinuation from the Study

Subjects must discontinue investigational product for any of the following reasons:

- Withdrawal of informed consent (subject's decision to withdraw for any reason)
- Any clinical AE, laboratory abnormality or intercurrent illness which, in the opinion of the
 investigator or sponsor, indicates that continued participation in the study is not in the best
 interest of the subject
- Pregnancy
- No migraine treated with study drug prior to the week 8 visit of the long-term treatment phase of the study
- Lack of efficacy of study medication

- Poor compliance with study procedures, including poor compliance with study medication dosing instructions.
- Infrequent study drug usage (defined as an average of <2 doses per month over 3 consecutive months).
- Please see Section 6.3.5 for guidance on study discontinuation based on results from the S-STS.
- eGFR \leq 40 (ml/min/1.73m²) using the estimated MDRD formula
- Termination of the study by Biohaven Pharmaceuticals
- Loss of ability to freely provide consent through imprisonment or involuntary incarceration for treatment of either a psychiatric or physical (e.g., infectious disease) illness

All subjects who discontinue should comply with protocol specified End of Treatment procedures as outlined in Table 1. The only exception to this requirement is when a subject withdraws consent for all study procedures or loses the ability to consent freely (i.e., is imprisoned or involuntarily incarcerated for the treatment of either a psychiatric or physical illness).

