1.2.4 Clinical Adverse Event Profile

1.2.4.1 Phase 2/3 Dose Ranging Study (BHV3500-201)

BHV-3500 is a concluded, pivotal, Phase 2/3, double-blind, randomized, placebo-controlled, dose-ranging study conducted to evaluate the safety and efficacy of zavegepant (5 mg, 10 mg, or 20 mg) of zavegepant intranasal (IN) versus placebo in the acute treatment of migraine.

No deaths were reported, and no treatment-related serious adverse events (SAEs) were reported. SAEs were reported on-treatment in two subjects including post-traumatic thrombosis reported in one subject in the zavegepant 10 mg group, and vestibular migraine reported in one subject in the placebo group. Both events were moderate in intensity and judged by the investigator as not related to study drug.

The overall incidence of AEs was 26.2% (311 of 1,185 subjects) in the zavegepant groups and 15.4% (62 of 403 subjects) in the placebo group. The incidence of AEs in the zavegepant groups were as follows: 22.7% (88 of 388 subjects) in the 5 mg group, 24.6% (97 of 394 subjects) in the 10 mg group, and 31.3% (126 of 403 subjects) in the 20 mg group. The majority of AEs in all treatment groups were mild or moderate in intensity, not related to study therapy and resolved without treatment. The most frequently (\geq 2%) reported AEs in any treatment group are shown in the table below.¹¹

BHV3500-20				eported in at l ient Group	Least Two Percent of
Adverse Event	5 mg	10 mg	20 mg	Overall zavegepant	Placebo
Dysgeusia	13.9%	13.5%	16.1%	14.5%	3.5%
Nausea	2.6%	4.1%	2.7%	3.1%	0.5%
Nasal Discomfort	1.3%	1.3%	5.2%	2.6%	0.2%
Throat Irritation	1.0%	.0% 1.0% 2.2% 1.4% 0.0%			0.0%
Nasal Congestion	0.3%	0.3%	2.0%	0.8%	0.5%
UTI	0.8%	1.0%	2.0%	1.3%	1.2%

Nasal inspection conducted at screening, baseline and end of treatment showed no clinical evidence of nasal mucosal injury. No subject had AST or ALT > 3x ULN or bilirubin > 2x ULN in any treatment group.

Refer to the most recent version of the Investigator Brochure for latest clinical adverse event profile.

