### 4.3 Subgroups

The following safety subgroups are of interest for the safety analysis set:

- Intrinsic factors
  - Age at informed consent (years):  $< 40$ ,  $\geq 40$ ,  $< 65$ ,  $\geq 65$
  - Sex: female, male
  - Race: White, Black or African American, other including Asian, Asian
  - Ethnicity: Hispanic or Latino, not Hispanic or Latino
  - Cardiovascular risk factors contraindicating triptans: yes, no (refer to the Zavegeptan Core SAP)
  - Baseline body mass index (BMI;  $\text{kg}/\text{m}^2$ ):  $< 25$ ,  $\geq 25$  to  $< 30$ ,  $\geq 30$

- Extrinsic factors
  - Average zavegepant exposure (sprays per month): < 6,  $\geq$  6 (see Section 6.2.5.1).
  - Cumulative zavegepant exposure (sprays): < 20,  $\geq$  20 to < 40,  $\geq$  40 to < 60,  $\geq$  60 to < 80,  $\geq$  80 (see Section 6.2.5.1)
  - Time on zavegepant (weeks): < 12,  $\geq$  12 to < 24,  $\geq$  24 to < 36,  $\geq$  36 to 48,  $\geq$  48 (see Section 6.2.5.1)
  - Concomitant prophylactic migraine medication use: yes, no (see Section 6.2.5.4)
  - Current or concomitant approved biologics use (yes, no; see Section 6.2.5.4)
  - Total treated migraine days per month in the overall LTT (< 2,  $\geq$  2; see Section 6.4.6.2).

Subgroup tables present results by subgroup level and overall for subjects with non-missing subgroup level data. Subgroup levels may be redefined or combined based on the availability of data.

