- $\geq 6$  sprays per month for 1, 2, 3, 4, 5,  $\geq 12$ ,  $\geq 6$ ,  $\geq 3$  and  $\geq 1$  months
- $\geq 7$  sprays per month for 1, 2, 3, 4, 5,  $\geq 12$ ,  $\geq 6$ ,  $\geq 3$  and  $\geq 1$  months
- $\geq 8$  sprays per month for 1, 2, 3, 4, 5,  $\geq 12$ ,  $\geq 6$ ,  $\geq 3$  and  $\geq 1$  months.
- Total zavegepant exposure (sprays) summed across all subjects, derived by summing cumulative exposure across all subjects
- Total zavegepant exposure (patient-years), derived by summing (study drug end date – study drug start date + 1)/365.25 across all subjects.

See Section 7.1 for derived dates.

eDiary zavegepant and LTT exposure is also tabulated by subgroup level and overall for the safety analysis set for all subgroups of interest described in Section 4.3.

Months are 4-week (28-day) intervals in the LTT analysis period defined as follows:

- Month 1 ( $\leq 4$  weeks; study days 1 to 28)
- Month 2 ( $> 4$  to  $\leq 8$  weeks; study days 29 to 56)
- Month 3 ( $> 8$  to  $\leq 12$  weeks; study days 57 to 85)
- Month 4 ( $> 12$  to  $\leq 16$  weeks; study days 85 to 112)
- Month 5 ( $> 16$  to  $\leq 20$  weeks; study days 113 to 140)
- Month 6 ( $> 20$  to  $\leq 24$  weeks; study days 141 to 168)
- Month 7 ( $> 24$  to  $\leq 28$  weeks; study days 169 to 196)
- Month 8 ( $> 28$  to  $\leq 32$  weeks; study days 197 to 224)
- Month 9 ( $> 32$  to  $\leq 36$  weeks; study days 225 to 252)
- Month 10 ( $> 36$  to  $\leq 40$  weeks; study days 253 to 280)
- Month 11 ( $> 40$  to  $\leq 44$  weeks; study days 281 to 308)
- Month 12 ( $> 44$  to  $\leq 48$  weeks; study days 309 to 336)
- Month 13 ( $> 48$  to  $\leq 52$  weeks; study days 337 to 364)
- Month 14 ( $> 52$  to  $\leq 56$  weeks; study days 365 to 392).

See Section 7.3 for the definition of study days.

Exposure categories assess the number of months in which a subject exceeded select spray counts in the LTT analysis period (see Section 7.2), where the number of months are not necessarily consecutive. For example, suppose a subject administers 4 sprays in Month 1, 3 sprays in Month 2, 5 sprays in Month 3, 6 sprays in Month 4, and 0 sprays in Month 5. Thus, this

subject is considered to have administered  $\geq 2$  sprays per month for 4 months (i.e., Months 1 through 4),  $\geq 4$  sprays per month for 3 months (i.e., Months 1, 3 and 4), and  $\geq 6$  sprays per month for 1 month (i.e., Month 4).

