#### 6.4.1.2 *AE Overview*

An AE overview without SOC and PT presents the number and percentage of subjects with any the following AEs: any AE; mild AE; moderate AE; severe AE; moderate or severe AE; AE related to study drug; AE leading to study drug discontinuation; SAE; SAE related to study drug; SAE leading to study drug discontinuation; potential drug abuse AE; medication-overuse headache AE; hepatic-related AE; local irritation AE; cardiovascular AE; and suicidality AE.

An AE overview is produced for each the following analysis periods and analysis sets:

- Pre-treatment AEs for the enrolled analysis set
- Pre-treatment AEs for the safety analysis set
- On-treatment AEs for the safety analysis set
- On-treatment AEs for the safety analysis set by subgroup level and overall for all subgroups of interest specified in Section 4.3
- TEAEs for the safety analysis set
- Follow-up AEs for the follow-up analysis set.

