#### 6.4.1.4 *On-treatment AEs*

On-treatment AEs are tabulated for the safety analysis set by SOC and PT for the following endpoints:

- AEs by intensity \*
- AEs occurring with  $\geq 5\%$  frequency by intensity (primary safety endpoint). The 5% cut applies only to total intensity.
- AEs occurring with  $\geq 10\%$  frequency
- TEAEs by intensity

- TEAEs occurring with  $\geq 2\%$  frequency after rounding. Percentages are displayed rounded to integers, and AEs are displayed in alphabetical order by SOC and PT.
- AEs related to study drug by intensity \*
- AEs by relationship to study drug (related, possibly related, unlikely related, not related, not reported)
- SAEs (primary safety endpoint)
- AEs leading to study drug discontinuation (primary safety endpoint)
- AEs of special interest
  - Potential drug abuse AEs, displayed in alphabetical order by intensity and PT without SOC (exploratory safety endpoint)
  - Medication-overuse headache AEs (exploratory safety endpoint)
  - Hepatic-related AEs by intensity (exploratory safety endpoint)
  - Local irritation AEs by intensity (exploratory safety endpoint)
  - Cardiovascular AEs
  - Suicidality AEs
- Exposure-adjusted multiple occurrences of unique AEs
- Exposure-adjusted multiple occurrences of unique SAEs
- Exposure-adjusted multiple occurrences of unique SAEs related to study drug
- Exposure-adjusted multiple occurrences of unique non-SAEs occurring with  $\geq 5\%$  frequency.

Endpoints marked with “\*” are also tabulated by subgroup level and overall for all subgroups of interest specified in Section 4.3.

Calculations for on-treatment exposure-adjusted multiple occurrences of unique AEs set the reference start date to the study drug start date, reference end date to the study drug end date, and reference last date to the study drug last date + 7 days.

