#### 6.4.6.2 *Treated Migraine Days per Month*

The number of treated migraine days per month is derived as follows:

- Month during LTT:
  - If the total number of study days in the month < 14: total number of treated migraine days in the month (i.e., no proration)
  - If the total number of study days in the month  $\geq 14$ :  $28 \times (\text{total number of treated migraine days in the month}) / (\text{total number of study days in the month})$
- Overall LTT:
  - If the total number of study days in the LTT analysis period < 14: total number of treated migraine days in the LTT analysis period (i.e., no proration)
  - If the total number of study days in the LTT analysis period  $\geq 14$ :  $28 \times (\text{total number of treated migraine days in the LTT analysis period}) / (\text{total number of study days in the LTT analysis period})$ .

All study days from LTT start to LTT end are included in analyses, not only days of data.

The following tables are produced for the safety analysis set:

- Number and percentage of subjects in the following categories based on the number of treated migraine days per month in the overall LTT by migraine intensity (total; moderate or severe): 0,  $> 0$  to  $< 1$ ,  $\geq 1$  to  $< 2$ ,  $\geq 2$  to  $< 3$ ,  $\geq 3$  to  $< 4$ ,  $\geq 4$  to  $< 5$ ,  $\geq 5$  to  $< 6$ ,  $\geq 6$  to  $< 7$ ,  $\geq 7$  to  $< 8$ ,  $\geq 8$ ,  $< 2$ ,  $\geq 2$ . The last 2 categories for total migraine intensity align with subgroups specified in Section 4.3.
- Number and percentage of subjects in the above categories based on the maximum number of treated migraine days per month in any 1 month during LTT by migraine intensity.

These tables are also produced for the safety analysis set with  $\geq 51$  weeks in the LTT analysis period (see Section 6.2.6.1).

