## 7.2 Analysis Periods

Analysis periods are defined as follows:

- OP: measurement date/time on or after the OP start date/time through the OP end date/time. This period is used to assess the number of migraine days per month during the OP.
- Pre-treatment: measurement date/time on or before the study drug start date/time. This period is used to derive baseline values, and to assess safety and outcomes research endpoints. Note that all measurements are pre-treatment for subjects in the enrolled analysis set with missing study drug start date.
- Pre-LTT: measurement date/time on or before the LTT start date/time. This period is used to derive analysis visit windows for slotting observations. Note that all measurements are pre-LTT for subjects in the enrolled analysis set with missing LTT start date.
- LTT: measurement date/time after the LTT start date/time through the LTT last date. This period is used to derive analysis visit windows for slotting observations, and to assess exposure and migraine days during LTT. Note that AEs with imputed start date equal to the

LTT start date are part of this period (refer to the Zavegeptan Core SAP for AE start date imputation).

- Follow-up: measurement date after the LTT last date. This period is used to slot observations.
- On-treatment safety: measurement date/time after the study drug start date/time through the study drug last date + 7 days. This period is used to assess safety endpoints on treatment.  
Note that AEs with imputed start date equal to the study drug start date are part of this period.
- Follow-up safety: measurement date after the study drug last date + 7 days. This period is used to assess safety endpoints during follow-up.

See Section 7.1 for derived dates for determining analysis periods. If measurement time is missing, not collected, or not applicable for a parameter, then the measurement date is compared to the derived date.

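### To the extent Protocol 6.6 is enforced, the SAP's <2 treated-days-per-month subgroup is mainly subjects stopped early, so its crude AE percentages compare unequal follow-up

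*Protocol*

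**What the plan says.** **Stopping rule.** Protocol 6.6 lists "Infrequent study drug usage (defined as an average of <2 doses per month over 3 consecutive months" among the reasons for which study drug must be stopped, alongside treating no migraine before the Week 8 visit. Section 7.4 also says that non-compliance with average monthly dosing will lead to termination. Sections 4.3.4 and 7.2.2 are softer: withdrawal for non-compliance or non-use is permitted, not required.

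**Subgroup.** SAP 4.3 includes "Total treated migraine days per month in the overall LTT", cut at 2. A treated migraine day is a migraine day with a zavegepant dose (SAP 6.4.6). Under SAP 6.4.6.2 the count is prorated to 28 days once LTT reaches 14 days, and "All study days from LTT start to LTT end are included in analyses, not only days of data".

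**AE tables.** The AE overview in SAP 6.4.1.2 covers "On-treatment AEs for the safety analysis set by subgroup level and overall for all subgroups of interest specified in Section 4.3". In SAP 6.4.1.4 the two starred tables (AEs by intensity; related AEs by intensity) "are also tabulated by subgroup level and overall for all subgroups of interest specified in Section 4.3". All are numbers and percentages of subjects. The four exposure-adjusted AE tables carry no star and are produced overall only.

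**Window.** SAP 7.2 defines the on-treatment safety period as "measurement date/time after the study drug start date/time through the study drug last date + 7 days".

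**Related displays.** SAP 6.2.6.1 states that "eDiary zavegepant and LTT exposure is also tabulated by subgroup level and overall for the safety analysis set", for every subgroup in 4.3. SAP 8 leaves this subgroup out of the interim CSR, so the point concerns the final CSR only.

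**The concern.** The subgroup is labelled as a monthly rate of use, but its cut lies on a stopping threshold. If low users are stopped at about Week 12, the <2 column describes short follow-up as much as infrequent dosing. A crude percentage of subjects with an AE grows with observation time, so this column can look safer than the ≥2 column when the underlying risk is the same. A reader could then take the gap as evidence that less frequent dosing causes fewer AEs.

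Time on zavegepant and cumulative sprays are also time-dependent subgroups in SAP 4.3, but their labels say so. This label does not.

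**Working it through.** **1. The plan's own figure.** For 0 events in 600 subjects, the exact one-sided 95% upper bound is 1 − 0.05^(1/600) = 0.00498, which matches the stated 0.005. It does not depend on this subgroup.

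**2. What full enforcement implies, from the documents alone.** A mean of <2 over 3 months is fewer than 6 doses in 3 months. Months 1–12 contain four separate 3-month windows, so a 52-week completer needs at least 4 × 6 = 24 doses. Month 13 can be empty: 6 doses in each of months 2, 5, 8 and 11 satisfies every 3-month window and the Week 8 rule. If each dose is a treated migraine day, 28 × doses / 364 gives:
- 24 doses: 1.85
- 25 doses: 1.92
- 26 doses: 2.00, already in the ≥2 group

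If LTT runs to day 371, 26 doses also fall below 2 (28 × 26/371 = 1.96). Nearly everyone else in the <2 group must have left early.

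**3. Size under full enforcement (simulation).** These inputs are assumptions, not in the documents:
- mean 2.5, 3.5 or 4.5 doses per 28 days, CV 30, 50 or 70%, gamma-distributed rates
- other dropout 0 or 25% per year
- the same AE risk in both groups, 60% at 1 year

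This gives 3 × 3 × 2 = 18 settings of 60,000 subjects. From the documents come the cap of 8 doses per 28 days, the Week 8 stop, and the stop for <6 doses in 84 days, checked every 4 weeks from Week 12. The early-AE variant places 24.6% of subjects' AEs at first dose. That borrows "24.6% (97 of 394 subjects) in the 10 mg group" (97/394 = 0.246), which is a whole-study incidence, so its placement at first dose is also an assumption.

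| | <2 | ≥2 |
|---|---|---|
| Share of treated subjects | 5–47% | 53–95% |
| Median LTT, weeks | 12 | 36–52 |
| Median on-treatment time, weeks | 7.9–9.6 | 32.6–51.6 |
| Crude AE %, constant hazard | 12.3–15.3 | 42.2–56.7 |
| Crude AE %, early-AE variant | 30.7–34.2 | 49.0–57.8 |

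Of the <2 group, 85–100% left under a 6.6 use rule. The within-setting crude ratio is 0.24–0.35 (constant hazard) or 0.55–0.66 (early AEs). A separately coded repeat gave 0.23–0.34 and 0.55–0.63.

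**4. Partial enforcement.** A second simulation assumed mean 3–5 doses per month, 10–30% other dropout per year and a constant 0.5 AEs per patient-year in everyone. The ratio is the <2 crude percentage over the ≥2 one; under full enforcement it runs from 8.3/35.1 = 0.24 to 9.4/31.1 = 0.30.

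| Share of 6.6 stops enforced | <2 group with <51 weeks in LTT | Crude AE ratio |
|---|---|---|
| 100% | 99.7–100% | 0.24–0.30 |
| 75% | 80–89% | 0.35–0.41 |
| 50% | 59–76% | 0.48–0.58 |
| 25% | 35–60% | 0.63–0.76 |
| 0% | 10–40% | 0.83–0.94 |

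The 100% row includes settings where only 90% of doses fall on migraine days; the other rows assume all do.

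**5. Other sensitivities (step 3 model, early-AE variant).**
- Half of those meeting a stop rule kept: 0.65–0.80. All kept: 0.80–1.00.
- Sites act one visit later: 0.61–0.72.
- 1-year risk 40%: 0.70–0.79. 80%: 0.51–0.61.
- 10% of subjects stop at their first AE: 0.61–0.85. 20%: 0.66–1.05.

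**6. Candidate corrections at equal risk, 6.6 followed (target ratio 1).**
- Subjects with an AE per on-treatment time, a first-event approximation to the SAP's exposure adjustment: 1.24–1.40 with constant hazard, 2.4–3.1 with early AEs.
- Kaplan-Meier estimate of any AE at 12 weeks from first dose, censored at last contact: 0.90–1.06 across both AE patterns. With early AEs and 10% stopping at their first AE it rises to 1.06–1.65.
- Only 53–68% of <2 subjects are observed for the full 12 weeks, against 95–100% of ≥2 subjects, so numbers at risk are needed.

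**The case against.** The case against acting is substantial, and much of it stands.

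- **Enforcement is uncertain.** The protocol is mandatory in one place and permissive in others. SAP 6.4.6.2 plans the same <2 and ≥2 categories for subjects with at least 51 weeks in LTT, so it provides for low users who stay. At 25% enforcement, early leavers are no longer a majority in most settings.
- **The time gap is already displayed.** Time in LTT, time on zavegepant and patient-years are tabulated by this subgroup. That discloses the imbalance but leaves the AE percentages as they are.
- **The tables are descriptive.** SAP 3.2 declares a while-on-treatment strategy, and no test or contrast between the columns is planned. This is one of 12 subgroups. Average sprays per month (<6, ≥6) shares the weakness in milder form.
- **Some material is not public.** The Core SAP and the mock tables are not available, and a suitable footnote may already exist there.

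Three stronger readings are tempting. A reader might infer that the <2 column will understate AEs by a known factor. The documents give no dosing, dropout or AE-timing data for this trial, and AE-driven stopping can bring the ratio to 1 or slightly above. A reader might infer that the SAP intends a dose-frequency comparison; it specifies none. A reader might also infer that exposure-adjusted tables by subgroup would repair the display. When AEs cluster early they over-correct: 2.4–3.1 is further from 1 on the log scale than 0.55–0.66.

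**Conclusion.** The point holds in conditional form. To the extent 6.6 is enforced, the <2 subgroup is mainly subjects stopped early, and its crude on-treatment AE percentages can be lower than those of the ≥2 group at equal risk. The composition under full enforcement follows almost entirely from the protocol's rule. The size of the AE gap does not: it rests on assumed use, dropout, AE risk and AE timing, and its direction is not certain when AEs cause stopping.

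The consequence is limited to how one descriptive subgroup is read in the final CSR. The overall AE tables, the primary safety endpoints and the 600-subject bound are unaffected. This is a minor improvement to presentation, not a defect in the primary analysis.

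**What to change.** Keep the planned tables in SAP 6.4.1.2 and 6.4.1.4 on their declared on-treatment window. For the <2 / ≥2 treated-days subgroup only:

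1. Add the Kaplan-Meier estimate of any AE at 12 weeks from first dose, censored at last contact, with numbers at risk. SAP 6.1.1.1 already names the method. Protocol 8.3.1 collects non-serious AEs through the follow-up safety visit, so no new data are needed. Required SAE collection ends 14 days after the last dose (Protocol 8.1.3), so SAE rows should stay in the planned tables only.
2. Footnote both displays: the groups are defined by post-baseline use, follow-up is unequal because of the 6.6 rule, and the columns are not a dose-frequency comparison.

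Exposure-adjusted subgroup tables are not recommended as the correction, because they over-correct when AEs cluster early.

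The cost is one extra display and a footnote. The display does not remove selection when AEs themselves cause stopping (1.06–1.65 with 10% stopping at their first AE and early AEs), so it should not appear without the footnote.
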